3.1 DESCRIPTION OF THE STUDY

The main study is a prospective, multicenter, open-label, single-arm effectiveness and safety study in patients with early stage RRMS. The first dose of ocrelizumab will be administered as an initial dose of two 300-mg infusions (600 mg total) in 250 mL 0.9% sodium chloride each separated by 14 days (i.e., Days 1 and 15) followed by one 600-mg infusion in 500 mL 0.9% sodium chloride every 24 weeks (± 14 days) for the remainder of the study duration.

Patients will be assessed for effectiveness and safety every 24 weeks as described in the Schedule of Assessments presented in Appendix 1.

The study will consist of the following periods:

- Screening period: Up to 4 weeks
- Treatment period: Open-label treatment period of 192 weeks (i.e. 24 weeks after the last dose of ocrelizumab, which will be administered at Week 168)
- A *safety* follow-up period of 48 weeks *after the last infusion of the study drug*, as explained below

Safety Follow-up Period: Patients who discontinue treatment early for any reason and patients who complete the study treatment period and do not continue in a separate long-term extension (LTE) study, will be followed up for 48 weeks after the last infusion of study drug. When patients begin an alternative treatment for MS (see section 4.4.1 "Prohibited Therapy"), they will be discontinued from the study.

Patients who discontinue study treatment and switch to commercially marketed ocrelizumab, either after completion of the 192 weeks Treatment Period or after early discontinuation of the 192 weeks Treatment Period, will not enter the safety Follow-up Period.

A structured telephone interview will be conducted by site personnel every 8 weeks between the study visits (starting after the site visit at 8 weeks) during the treatment period to identify and collect information on any changes in the patient's health status that warrant an unscheduled visit (including new or worsening neurological symptoms) and possible events or infections.

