3.1.1 Overview of Study Design

Figure 1 presents an overview of the study procedures. A schedule of assessments is provided in Appendix 1.

Figure 1 Overview of Study Procedures

MRI = magnetic resonance imaging; OCR = ocrelizumab; NEDA = no evidence of disease activity

3.1.2 Screening

After providing written informed consent, patients will enter a screening period (up to 4-weeks) to be evaluated for eligibility.

Re-screening of patients is allowed in this protocol.

3.1.3 Treatment Period

Eligible patients will be treated with an initial dose of two 300-mg infusions (600 mg total) in 250 mL 0.9% sodium chloride each separated by 14 days (i.e., Days 1 and 15) followed by one 600-mg infusion in 500 mL 0.9% sodium chloride every 24 weeks (±14 days) for the remainder of study duration.

Ocrelizumab—F. Hoffmann-La Roche Ltd 34/Protocol MA30143, Version 10.0

Additional patients enrolled into the shorter infusion sub-study were randomized into 2 groups at week 24 visit. One group received 600 mg ocrelizumab in 500 mL 0.9% sodium chloride infused over approximately 3.5 hours every 24 weeks (±14 days) for the remainder of the study duration (as in the main study) and the other group received 600 mg ocrelizumab in 500 mL 0.9% sodium chloride infused over 2.0 hours followed by 100 mL 0.9% sodium chloride given as a slow infusion over the remaining 1.5 hours, in order to mimic the standard-length infusion (3.5 hour) starting from week 24 for the remainder of the study duration. Please see Appendix 10 for further details. Patients already enrolled in the main study were offered to participate in the shorter infusion substudy and were randomized into the above 2 groups at the next main study visit if found eligible and after providing written informed consent. The protocol amendment version 8.0 marked the completion of the shorter infusion substudy and patients will continue under the main study protocol.

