Based on the results of the primary analysis of the shorter infusion substudy, patients will be allowed to switch from the conventional ocrelizumab infusion (~3.5 hours) to the shorter ocrelizumab infusion (~2.0 hours) at any visit after the Week 24 visit based on the schedules of infusion as per the protocol, after providing written informed consent and in agreement with their treating physician, provided they have not experienced any previous serious IRRs with ocrelizumab treatment. While on the shorter infusion, the patients can switch back to the conventional infusion, in agreement with their treating physician. If patients develop a serious IRR while on the shorter infusion, they will be switched to the conventional infusion and should not be restarted on the shorter infusion at any following infusion visit.

*All l*aboratory samples can be taken up to 2 weeks prior to the scheduled study visit. Local laboratory results for hematology, biochemistry and CD4 should be available prior to dosing as they are re-treatment criteria. Local laboratory results for CD8 and CD19 may be available later, as they do not need to be verified prior to re-treatment. Samples for NfL, anti-drug antibodies (ADA), and ocrelizumab concentration are collected and sent to the central laboratory for analysis. Please see Section 4.5.8 for further details

After the end of treatment period visit of the last enrolled patient, approximately 24 weeks and 48 weeks may be needed to allow the confirmation of the last event of the 24-week and 48-week CDP (CDP/CDI confirmation visit). For those patients presenting with an EDSS change at the end of the treatment period and who roll over to the LTE study (Study MN39158), the 24-week and 48-week CDP confirmation visits will occur during the LTE study (Study MN39158). For patients who discontinue the study (e.g., move onto commercial ocrelizumab, or start treatment with another DMT), the EDSS CDP confirmatory assessments will not be performed.

Sub-studies will be conducted in selected countries according to local approvals and procedures. Please refer to Appendices 8, 9, and 10 for the sub-study protocols.

Criteria for Re-Treatment with Ocrelizumab

Prior to re-treatment with ocrelizumab, patients will be evaluated for the following conditions and laboratory abnormalities. If any of these are present prior to re-dosing, further administration of ocrelizumab should be suspended until these are resolved or withheld indefinitely:

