- Life threatening (Common Terminology Criteria for Adverse Events [CTCAE] Grade 4) infusion-related event that occurred during a previous ocrelizumab infusion
- Current active infection other than a fungal nailbed infection. The re-treatment should be delayed until the active infection is treated and patient fully recovered
- CD4 cell count < 250/µL
- Absolute neutrophil count (ANC) <1.0 × 10³/µL
- Elevated aspartate aminotransferase (AST)/ serum glutamic oxaloacetic transaminase (SGOT) or alanine aminotransferase (ALT) /serum glutamic pyruvic transaminase (SGPT) (>3 × the upper limit of normal [ULN]) in combination with either an elevated total bilirubin (>2 × ULN) or clinical jaundice
- Hepatitis B screening tests prior to ocrelizumab administration
 - If total hepatitis B core antibody (HBcAb) was positive at screening, hepatitis B virus (HBV) deoxyribonucleic acid (DNA) measured by polymerase chain reaction (PCR) must be negative in order for a patient to be dosed with ocrelizumab. For patients with negative hepatitis B surface antigen (HBsAg) and positive total HBcAb, HBV DNA testing (by PCR) must be repeated every 24 weeks and evaluated prior to ocrelizumab administration. If it becomes positive, treatment with ocrelizumab must be discontinued and the patient should enter the safety follow-up.
- Any significant or uncontrolled medical condition or treatment-emergent, clinically significant laboratory abnormality
- Ongoing pregnancy or breastfeeding (In case of unplanned pregnancy, treatment should be interrupted, however the patient will remain in the trial and will have the opportunity to re-start ocrelizumab treatment after birth and breastfeeding are over. The total duration of treatment period will be 192 weeks from the date of first dose of ocrelizumab, irrespective of how long the treatment was interrupted due to pregnancy. During pregnancy and breastfeeding, the patient will continue to come for the regular scheduled visits (whenever possible, adhering to the time of scheduled visits as per protocol) and will perform all assessments except MRI.

At the end of the study treatment the patients will be encouraged to be included in a separate LTE (MN39158) study, as applicable, to further evaluate the effectiveness and safety of *ocrelizumab treatment*. This LTE will also aim to evaluate the long-term outcomes with ocrelizumab treatment over the extended period of time in patients with MS.

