The patient will need to remain at the clinic at every visit for at least 1 hour after the completion of the infusion for observation. After completion of the infusion, the IV cannula should remain in situ for at least 1 hour to allow for administration of drugs intravenously, if necessary, in the event of a delayed reaction. If no adverse events occur during this period of time, the IV cannula may be removed and the patient may be discharged.

See the Ocrelizumab IB and Drug Preparation Guidelines for detailed instructions on drug preparation, storage, and administration.

An overview of the ocrelizumab dosing is presented in Table 2 and the infusion rates for the conventional and the shorter infusions in Table 3.

	1st Dose ^{a,c}		2nd Dose ^{b,c}	3rd Dose ^{b,c}	4th Dose ^{b,c}	5th Dose ^{b,c}	6th Dose ^{b,c}	7th Dose ^{b,c}	8th Dose ^{b,c}
						(Weeks			
			(Weeks	(Weeks	(Weeks	96 - 120	(Weeks	(Weeks	(Weeks
			$24 - 48 \pm$	48 – 72 ±	72 – 96 ±	± 14	120 - 144	144 – 168	168 – 192
	(Weeks 1 – 24)		14 days)	14 days)	14 days)	days)	± 14 days)	± 14 days)	± 14 days)
	Day 1	Day 15	Week 24	Week 48	Week 72	Week 96	Week 120	Week 144	Week 168
Group	Infusion	Infusion	Infusion	Infusion	Infusion	Infusion	Infusion	Infusion	Infusion
Ocrelizumab	300 mg IV	300 mg IV	600 mg IV	600 mg IV	600 mg IV	600 mg IV	600 mg IV	600 mg IV	600 mg IV
	in 250 mL	in 250 mL	in 500 mL	in 500 mL	in 500 mL	in 500 mL	in 500 mL	in 500 mL	in 500 mL
	0.9%	0.9%	0.9%	0.9%	0.9%	0.9%	0.9%	0.9%	0.9%
	sodium	sodium	sodium	sodium	sodium	sodium	sodium	sodium	sodium
	chloride	chloride	chloride	chloride	chloride	chloride	chloride	chloride	chloride

Table 2 Overview of Ocrelizumab Dosing

IV=intravenous.

Note: Before each infusion of ocrelizumab, 100 mg of methylprednisolone IV and an antihistaminic drug will be administered to reduce the potential for infusion-related reactions. Each dose has a duration of 24 weeks. The open-label treatment period consists of 192 weeks of treatment; patients will receive a maximum of 8 doses.

- ^a The first dosing will consist of two IV infusions separated by 14 days (i.e., Days 1 and 15).
- ^b Beginning with the second dose, a single infusion of ocrelizumab will be administered.
- ^c Prior to the next infusion, a clinical evaluation will be performed to ensure that the patient remains eligible for retreatment.

Table 3 Ocrelizumab infusion rates for Conventional and Shorter Infusionsin absence of IRRs

Time (min)	S	horter infusio	on	Conventional infusion			

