1. BACKGROUND

1.1 RATIONALE FOR THE SUBSTUDY

Ocrelizumab is administered by intravenous infusion as a 600 mg dose every 6 months. The first ocrelizumab dose of 600 mg is always administered as a divided dose (2 x 300 mg infusions administered 14 days apart) to help reduce the incidence of infusion-related reactions (IRRs) which is highest upon the first infusion of ocrelizumab. The incidence and severity of IRRs is also higher upon the first infusion of all other B-cell depleting agents. The subsequent doses of ocrelizumab are administered as a single 600 mg infusion, with a minimum interval of 5 months to be maintained between each dose of ocrelizumab.

IRRs are among the most frequent adverse events associated with ocrelizumab treatment. During the Phase III relapsing multiple sclerosis (RMS) controlled treatment period, the incidence of IRRs in patients receiving ocrelizumab was highest during the first infusion (Dose 1, Infusion 1; 27.5% of RMS OPERA I and II [WA21092 and WA21093] patients pooled), and with subsequent dosing IRRs occurred with decreasing incidence. After the first dose, the incidence (RMS OPERA I and II pooled: 4.7% to 13.7% of patients), severity (Grade 1 or 2; RMS OPERA I and II pooled: 92.6% of patients) and symptoms (in >= 10% of RMS patients with IRRs: pruritus, rash, throat irritation and flushing) of IRRs were similar in both studies.

A preliminary analysis was performed on an ad-hoc data cut (06-April-2018) in the main study (ENSEMBLE) including 675 patients who had received the first infusion of dose 1 and 172 who had received dose 2 at week 24. The proportions of patients with IRRs were 28.7% and 12.2% at dose 1 and dose 2, respectively, which were similar to the rates of 27.5% and 13.5% observed in OPERA I and II pooled.

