## 4.5.1 Exposure to Study Medication

Within the substudy, in both randomized groups ocrelizumab is given as single infusions of 600mg at 24-week intervals. The only difference between the randomized groups is the duration of the infusion.

Patients will be considered to have received a dose of treatment if at least part of that infusion was given. If a dose is completely missed instead of delayed, the next dose number will be based on the number of previous doses received.

For each patient, the length of exposure to randomized treatment is from the date on which the patient first received randomized treatment (Substudy Day 1) until the last known alive date or CCOD, whichever is earlier. For patients who withdrew early from randomized treatment, the exposure is until the last known alive date (i.e., duration of exposure is equivalent to duration of observation period, and these terms are used interchangeably in this SAP). To summarize, the duration of exposure for a patient will be calculated as:

(Date of last contact\* – date of 1st Randomized Dose) + 1

\* Earlier of 1) date of CCOD 2) last known alive date

The following aspects of exposure to ocrelizumab will be summarized by randomized group:

- Treatment duration (weeks): frequency counts (number of patients and percentage) for 0-23 weeks, 24-47 weeks and 48-71 weeks will be presented
- Number of doses received: frequency counts (number of patients and percentage) and summary statistics (mean, SD and median) will be presented
- Total cumulative dose (derived to mg): summary statistics (mean, SD, median, lower and upper quartiles, minimum and maximum) will be presented

- Ocrelizumab infusion duration (minutes): summary statistics (mean, SD, median, lower and upper quartiles, minimum and maximum) will be presented by Randomized Dose and overall (all randomized doses).
- The number and percentage of infused patients with < 80% and ≥ 80% of the planned infusion volume will be presented, along with the number and percentage of infused patients who were pre-treated with methylprednisolone (or equivalent) only, with antihistamine only and with both methylprednisolone (or equivalent) and antihistamine. These summaries will be presented by Randomized Dose and then by Dose within Randomized Dose (and overall within Randomized Dose i.e. across all Doses).

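### The protocol states a 5-month minimum between ocrelizumab doses in Appendix 10, but its dosing schedule omits that limit, and on one reading of the visit windows, or after a delayed dose, permits a shorter gap

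*Protocol*

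**What the plan says.** **The minimum.** Appendix 10 Section 1.1, in describing how doses after the first are given, says they are single 600 mg infusions "with a minimum interval of 5 months to be maintained between each dose of ocrelizumab". The sentence appears once, in the background of the shorter-infusion substudy.

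**The schedule.** Section 3.1.3 gives the infusions "every 24 weeks (±14 days) for the remainder of study duration". Sections 3.1 and 4.3.2.1 and Appendix 1 footnote t repeat the 24-week interval with the same tolerance. Table 2 and Appendix 1 label the 600 mg infusions by study week (24, 48, 72, 96, 120, 144, 168), and Appendix 1 gives each visit its own ±14-day window. Section 3.1 ends treatment at Week 192, "24 weeks after the last dose of ocrelizumab, which will be administered at Week 168". The note to Table 2 adds that "patients will receive a maximum of 8 doses". None of these places states a minimum gap or refers to Appendix 10 for one.

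**Delays.** Under the re-treatment criteria in Section 3.1.3, if a listed condition is present, "further administration of ocrelizumab should be suspended until these are resolved or withheld indefinitely". For active infection, "The re-treatment should be delayed until the active infection is treated and patient fully recovered". No upper limit is set, and the timing of the following dose is not addressed. The substudy SAP recognises delays in Section 4.5.1, but its rule concerns dose numbering: "If a dose is completely missed instead of delayed, the next dose number will be based on the number of previous doses received".

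**The concern.** A window around each visit and a minimum interval between visits both limit dose spacing. Here they stand in different parts of one protocol with no link between them. Staff working from Section 3.1.3, Table 2 and Appendix 1 would not meet the minimum at all.

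There are two distinct gaps. First, windows placed around fixed weeks let consecutive visits move towards each other by up to 28 days. Second, a dose held under the re-treatment criteria moves later, while the text is silent on whether the next dose moves with it.

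At stake are the actual spacing of 600 mg doses in an ongoing trial, and the classification of a short gap. The text does not settle whether two in-window infusions closer than 5 months would be a protocol deviation under Section 9.2, or would bear on the per-protocol population in Section 6.

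**Working it through.** This is date arithmetic; no sample-size formula applies.

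**The plan's own calendar.** One split first dose plus infusions at Weeks 24, 48, 72, 96, 120, 144 and 168 makes 1 + 7 = 8 doses, and 168 + 24 = 192 weeks. Both figures match the protocol.

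**Inputs.** Interval: 24 weeks = 168 days. Tolerance: ±14 days (Section 3.1.3, Appendix 1). Minimum: 5 months (Appendix 10 Section 1.1). The protocol does not define a month. Over all start dates in a four-year cycle, five calendar months last 150 to 153 days, with a mean of 152.2.

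**Reading A: windows around fixed study weeks.** The shortest gap is one dose at +14 days and the next at −14 days:

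168 − 14 − 14 = 140 days (20 weeks, about 4.6 months)

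An example is infusions at Weeks 50 and 70. The shortfall is 150 − 140 = 10 to 153 − 140 = 13 days. The same holds for all six consecutive pairs of 600 mg doses, from Weeks 24/48 to Weeks 144/168.

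**Reading B: tolerance counted from the previous dose.** The shortest gap is:

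168 − 14 = 154 days (about 5.06 months)

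This meets the minimum with 1 to 4 days to spare. However, two successive intervals of +14 days put the Week 48 dose 28 days late, outside its own ±14-day window. Seven put the Week 168 dose 7 × 14 = 98 days late, at Week 182, only 10 weeks before the Week 192 end point that Section 3.1 places 24 weeks after the last dose.

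**After a delay of D days.** If the next dose is given on its calendar week, the gap is 168 − D. If it is given at the early edge of its window, the gap is 154 − D.

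| Delay D (days) | Next dose on calendar week | Next dose 14 days early |
|---|---|---|
| 14 | 154 | 140 |
| 16 | 152 | 138 |
| 21 | 147 | 133 |
| 28 | 140 | 126 |
| 42 | 126 | 112 |

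On the calendar week, the gap falls below 5 months when D exceeds 168 − 152.2 = 15.8, or about 16 days (15 to 18 across the 150-to-153-day range). At the early edge the figure is 154 − 152.2 = 1.8, or about 2 days (1 to 4). If the next dose is instead timed at 24 weeks ±14 days from the actual last infusion, the gap is at least 154 days whatever the delay, and the later doses leave the calendar.

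**The case against.** The strongest reply is Reading B. The wording in Section 3.1.3 attaches the tolerance to the interval between infusions, and on that reading no in-window pair falls below five calendar months. This stands as far as it goes: no passage states outright that every infusion date is counted from the first dose. The one sentence that looks like it, "The total duration of treatment period will be 192 weeks from the date of first dose of ocrelizumab", belongs to the pregnancy rule and concerns the length of the treatment period. The fixed-week reading is an inference from the week labels, the per-visit windows and the Week 168/192 end point. But Reading B does not reconcile the text either, because it lets doses leave the Appendix 1 windows.

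Second, a window and a minimum can both apply, and a site can meet both by not dosing early after a late visit. That is correct, and it is why a reader who infers that the protocol instructs a breach goes too far. The dosing sections are silent on the minimum; they do not override it.

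Third, the minimum is a single background sentence for a substudy completed at protocol version 8.0. That weakens it as an operative rule. It nevertheless describes ocrelizumab dosing in general, Appendix 10 Section 3.3.1 says dose and schedule are unchanged in the substudy, and the sentence remains in Version 10.0.

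Fourth, a month of 28 days would make 140 days exactly sufficient. Even then, a delay of more than 28 days followed by a calendar-week dose gives less than 140.

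Finally, Section 4.3.2.1 sends sites to the Investigator's Brochure and Drug Preparation Guidelines, which are not available here. They may hold spacing guidance. The re-treatment criteria are also rechecked before every dose, including the one after a delay.

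**Conclusion.** The protocol is unreconciled on dose spacing. Under the fixed-week reading, two consecutive in-window 600 mg doses can be 140 days apart, 10 to 13 days short of the stated minimum. Under the interval reading there is no conflict from the windows alone, but the per-visit windows cannot then be kept after successive late doses. The delay problem arises if the next dose returns to its calendar week: a delay beyond about 16 days takes the gap below 5 months. These results rest on calendar months of 150 to 153 days and, for the 140-day figure, on the inferred fixed calendar.

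Three stronger inferences are not supported:

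- **A rate of short gaps.** With day offsets from −14 to +14 at each of two visits, 55 to 91 of the 29 × 29 = 841 combinations (6.5% to 10.8%) fall short. That counts permitted combinations and is not a probability. Treating dosing days as uniform and independent would be needed to make it one, and the documents give no basis for either.
- **That short gaps would go unrecorded, or that sites would diverge.** The documents do not say how such a gap would be classified or how sites schedule after a late visit.
- **That patients with a delayed dose are the ones for whom close spacing matters most.** That is a clinical claim with no source in the text.

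What remains is more than missing detail, because on a well-supported reading a stated window permits a gap below a stated minimum. It should be corrected.

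**What to change.** Reconcile the interval statement in Appendix 10 Section 1.1 with Section 3.1.3, Section 4.3.2.1, Table 2 and the Appendix 1 windows, so that one rule applies in all of them. In Section 3.1.3, state (a) whether the ±14-day window is counted from the last actual infusion or from the calendar week, and (b) which of these times the next infusion after a dose delayed under the re-treatment criteria. If a minimum interval is kept, define its unit in days or weeks and say whether falling below it is a protocol deviation. Which rule stands is for the sponsor to decide.

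The cost is wording in those places and a site memo. The small downside is that some infusions may separate from the nominal visit week.
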